-------------------------------	--

	
(4) Receipt of any experimental treatment for COVID-19 (off-label, compassionate use, or study-related) within the 30 days prior to the time of the screening evaluation(5) Any excluded concomitant medication as described in the ARAKODA package insert [Section 15.1](6) Any COVID-19 symptoms which, in the opinion of the investigator, is suggestive of possible requirement to hospitalize within 48 hours of enrollment(7) Positive pregnancy test(8) Have been symptomatic for more than five days when the first dose would be administered
Treatment Groups:	There will be 2 treatment groups; TQ and placebo for which at least 250 patients will be randomized in 1:1 ratio to treatment with clinical site as a stratification variable. Randomizations will continue until at least 250 patients meet the criteria for mITT.
Screening Procedures:	After signing informed consent, patients will be screened for eligibility including medical history, G6PD, RT-PCR for SARS-CoV-2, pregnancy testing for females of child-bearing potential, hematology, blood chemistry, vital signs, O ₂ saturation, and physical exams. The Screening period will be a maximum of 4 days (Days -4 to -1), and the first day of dosing will be Study Day 1.
Randomization Procedure:	Eligible patients will be randomized at a 1:1 ratio to receive TQ or placebo. Randomization will be performed through a centralized, web-based, validated system that automates the assignment of patients to treatment allocation. Randomization will be stratified by clinical site.
Efficacy Assessments:	
• Clinical signs and symptoms of COVID-19 (clinically diagnosed and patient reported) including fever, shortness of breath, cough, and respiratory rate daily from Day 1 to Day 28 (Note, the clinical signs of COVID-19 will not be reported as AEs)• SARS-CoV-2 PCR at Day 12 ± 1 day.• Hospitalization

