Safety and Tolerability Assessments:	Clinical: 
• Vital signs (blood pressure, heart rate, and O₂ saturation)• AEs Laboratory: 
• Hematology: red blood cells (RBC), white blood cells (WBC) with partial differential (neutrophils), hematocrit, hemoglobin, platelets; C-reactive protein (CRP), international normalized ratio (INR), prothrombin time (PT)/ partial thromboplastin time (PTT)• Blood chemistry: blood urea nitrogen (BUN), creatinine, alanine transaminase (ALT), and aspartate aminotransferase (AST)• Pregnancy test
Statistical Analysis:	Analysis Populations: 
• The modified Intention-to-Treat (mITT) population will include all patients who took at least one dose of study medication and had at least one post baseline assessment. The mITT population will be analyzed as they are randomized, regardless of which treatment a patient received.• Safety population: Any patient randomized and received any dose of study drug. Safety population will be analyzed based on the actual treatment received.• The PP population includes all mITT patients who completed the Day 12 clinic visit without any major protocol deviations. Protocol deviation category (minor or major) will be determined prior to the database lock and unblinding.

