On Day 1, eligible patients will either return to the clinic or may have a telemedicine visit. Continued eligibility will be reviewed, and if still eligible, patients will be randomized and will receive and self-administer 200 mg TQ or matching placebo on Days 1, 2, 3, and 10 (each administration of drug will be within \pm 1 day with the exception of the first dose). If the Day 1 visit is a telemedicine visit, the randomized blinded study drug will be couriered to the patient. Patients will be provided an oral thermometer to check and record their daily temperature and a home pulse oximeter to record their daily oxygen saturation. Patients will also be provided with an electronic study diary (eDiary) (loaded onto a device of their choosing) and be required to complete the eDiary entries from Day 1 through Day 12 [\pm 1 day]. Patients will record respiration rate, temperature, COVID-19 clinical signs including presence and severity of cough, respiration rate and shortness of breath, AEs, and concomitant medications in the electronic diary daily. They will also record study drug administrations in the diary to monitor compliance. Daily diary data will be automatically uploaded to the electronic data management system and will be reviewed daily by clinical staff.

Patients will be contacted by telephone or videoconferencing by designated study personnel on a daily basis to review AEs for severity by asking an open ended question, check for use of concomitant medications, and if there are new or worsening signs and symptoms of COVID-19 disease from Day 1 through Day 11 [\pm 1 day]. Telemedicine interviews will follow a script and information will be recorded in source documents. If a suspected SAE or worsening of signs and symptoms of COVID-19 are reported, a study physician will be contacted to determine if the patient needs additional support (clinic visit, medication, or emergency room visit). If the patient cannot be reached an individual from their emergency contact list will be contacted to determine if the patient has been hospitalized. Patients will return to clinic on Day 12 [\pm 1 day] for the assessments listed in [Table 1](#). From Day 13 [\pm 1 day] through Day 28 [\pm 1 day], patients will be instructed to complete the eDiary and will have a final telemedicine call on Day 28 [\pm 1 day].

The schedule of study procedures is illustrated in [Table 1](#).

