6.1.1 Study Duration Per Patient

The total duration of the study will be up to 33 days for each patient, including 4 days for screening on Days -4 to -1, self-administration of study drug on Days 1, 2, 3, and 10, daily recording and remote collection of signs and symptoms from Day 1 through Day 11, an in-clinic visit on Day 12, and a telemedicine call on Day 28 ± day to assess AEs and clinical recovery.

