7.3 Withdrawal Criteria

Patients are free to withdraw from the study at any time, without prejudice to their continued care.

Patients should have their Investigational Product withheld and continue to be followed for Safety per the protocol should any of the following events occur:

1. Patient develops an illness that would interfere with his/her continued participation.
2. Patient is noncompliant with the study procedures or medications in the opinion of the investigator. Patients who receive at least 1 dose of study drug should be followed for safety, if possible, until Day 28.
3. Patient takes prohibited concomitant medications as defined in this protocol.
4. There is confirmation of a pregnancy during the study, as evidenced by a positive pregnancy test.
5. The sponsor or a regulatory agency requests withdrawal of the patient.

Investigators should attempt to obtain information on patients in the case of withdrawal. For patients considered as lost to follow up, the investigator should make an effort (at least 1 phone call and 1 written message to the patient), and document his/her effort (date and summary of the phone call and copy of the written message in the source documents), to complete the final evaluation. All results of these evaluations and observations, together with a narrative description of the reason(s) for removing the patient, must be recorded in the source documents. The case report form (CRF) must document the primary reason for withdrawal.

If patients are hospitalized during the study period for anything other than being administratively registered in the hospital for observation, efforts should be made to continue the patient in the study

through Day 28. The Medical Monitor should assess the patient's ability to continue receiving study drug.

Investigators should contact the Medical Monitor, whenever possible, to discuss the withdrawal of a patient in advance.

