8.10.2 Prohibited Concomitant Treatments (Medications and Therapies)

Prohibited concomitant medications include:

- Targeted COVID-19 therapeutics or therapies including remdesivir, dexamethasone, and convalescent plasma
- OCT2 and MATE substrates (e.g., dofetilide, metformin). If coadministration cannot be avoided, monitor for drug-related toxicities and consider dosage reduction if needed based on approved product labeling of the coadministered drug

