12.2 Analysis Populations for Analyses

Three patient populations will be defined:

- The modified Intention-to-Treat (mITT) population will include all patients who took at least one dose of study medication and had at least one post start of treatment assessment. The mITT population is analyzed as randomized, regardless of which treatment a patient received.
- Safety population: Any patient randomized and received any dose of study drug. Safety population is analyzed based on the actual treatment received.
- The PP population includes all mITT patients completing the Day 12 [± 1 day] in clinic visit without any major protocol deviations. Protocol deviation category (minor or major) will be determined prior to the database lock and unblinding.

Efficacy endpoints will be analyzed for the mITT population. Analyses of efficacy endpoints in the PP population will provide supportive evidence. Safety summaries will be based on the Safety population.

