12.3 Planned Efficacy Analyses

12.3.1 Analysis of the Primary Efficacy Variable

The proportion of patients with clinical recovery at Day 12 will be analyzed using two methods: a 2x2 contingency table and logistic regression. The contingency table will provide unadjusted estimates of the proportions of patients with clinical recovery at Day 12. Copper-Pearson exact 95% confidence intervals around the recovery proportion within each treatment group will be provided. If 95% or more patients on the TQ arm have clinically recovered, then no logistic regression will be performed due to too few events then a Fisher's exact test will be used to compare treatment groups. However, if the rate is less than that then a logistic regression will be utilized. Treatment group will be the primary independent factor in the logistic regression. Additional covariates will be included in the model for every 10 events observed (eg, if at least 20 events then clinical site will be included, at least 30 events dichotomized number of symptoms (1-2 vs 3-4). Selection of additional covariates will be based on their relationship to the primary endpoint and correlation with other covariates. Patients who do not have a Day 12 visit due to hospitalization for COVID-19 symptoms will be considered treatment failures.

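### The per-protocol population drops every patient scored as a failure because COVID-19 hospitalisation prevented the Day 12 visit, so the supportive analysis excludes on outcome (minor)

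*Combined protocol and SAP*

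**What the plan says.** Section 12.3.1 and the Synopsis give one rule for an absent Day 12 outcome: "Patients who do not have a Day 12 visit due to hospitalization for COVID-19 symptoms will be considered treatment failures".

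The Synopsis defines the per-protocol set as follows: "The PP population includes all mITT patients who completed the Day 12 clinic visit without any major protocol deviations". Section 12.2 has the same requirement and adds the window of one day either side. Neither place makes an exception for patients whose outcome is already fixed by the hospitalisation rule.

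Section 12.2 makes mITT the efficacy population; it needs one dose and one assessment after the start of treatment, not a Day 12 visit. PP has a secondary role: "Analyses of efficacy endpoints in the PP population will provide supportive evidence".

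Two other passages bear on the point. Section 7.3 says of hospitalised patients that "efforts should be made to continue the patient in the study" through Day 28. Section 8.10.2 lists as prohibited "Targeted COVID-19 therapeutics or therapies including remdesivir, dexamethasone, and convalescent plasma".

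**The concern.** A patient failed by the hospitalisation rule has, by definition, no Day 12 clinic visit. The same fact that makes the patient a failure in mITT removes the patient from PP. A patient who attends on Day 12 still febrile or short of breath is also a failure but stays in PP. The supportive set thus loses one kind of failure, probably the sickest, and keeps the other.

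This exclusion is not about adherence to treatment, which is what a PP set is usually meant to isolate. If hospitalisations preventing the visit fall mainly on placebo, PP tends to understate the benefit of tafenoquine; if they fall mainly on tafenoquine, PP flatters it. At stake is how far the PP result can be read as support for the mITT result.

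**Working it through.** **The plan's own figure.** Section 12.6 states 80% power for 85% versus 70% with 125 per group, two-sided 0.05, by logistic regression. Wald test on the log odds ratio:

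- d = ln(0.85/0.15) − ln(0.70/0.30) = 0.887
- SE = √[1/(125·0.85·0.15) + 1/(125·0.70·0.30)] = 0.318
- power = Φ(0.887/0.318 − 1.96) = 79.8%

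The stated 80% reproduces and is not in question.

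**Inputs.** 125 per group at 85% and 70% gives 106.25 and 87.5 recoveries, rounded to 106 and 88. The mITT difference is 106/125 − 88/125 = 14.4 points. The numbers removed, h₁ (tafenoquine) and h₀ (placebo), are assumptions.

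**Formula.** Rule-based failures leave the denominator only:

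PP difference = R₁/(125 − h₁) − R₀/(125 − h₀)

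The p-value is from the log-odds Wald test: z = [ln(a/b) − ln(c/d)] / √(1/a + 1/b + 1/c + 1/d), where a, b are recovered and not recovered on tafenoquine and c, d the same on placebo.

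| Removed, TQ/placebo | PP calculation | Difference (points) | p |
|---|---|---|---|
| 0/0 (mITT) | 106/125 − 88/125 | 14.4 | 0.0071 |
| 2/6 | 106/123 − 88/119 | 12.2 | 0.0186 |
| 1/3 | 106/124 − 88/122 | 13.4 | 0.0115 |
| 2/2 | 106/123 − 88/123 | 14.6 | 0.0058 |
| 4/4 | 106/121 − 88/121 | 14.9 | 0.0045 |
| 3/1 | 106/122 − 88/124 | 15.9 | 0.0028 |
| 6/2 | 106/119 − 88/123 | 17.5 | 0.0009 |

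**No true difference (88/125 in both arms).**

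- 1/3 removed: 88/124 − 88/122 = −1.2 points; 3/1 gives +1.2
- 2/6 removed: 88/123 − 88/119 = −2.4 points; 6/2 gives +2.4
- equal removals: 0

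The smallest p-value here is 0.67. In every case in both sets, PP leads to the same conclusion as mITT.

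**How far that depends on small counts.** Take an assumed extreme of 10% removed on placebo and 2% on tafenoquine (12.5 and 2.5 patients). PP is then 0.85/0.98 − 0.70/0.90 = 0.867 − 0.778, or 9.0 points. With 122.5 and 112.5 patients, z = (1.878 − 1.253)/0.350 = 1.79, p about 0.07. A large and lopsided removal could therefore separate PP from mITT. Nothing in the documents gives a rate of that size.

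**The case against.** The strongest reply is that this hardly matters. mITT carries the efficacy conclusion and keeps these patients as failures. Requiring the key visit is a common PP convention. Numbers should be low: Section 7.2 excludes severe illness and anyone judged likely to need admission within 48 hours, and only hospitalised patients who also miss Day 12 are affected. In all the small-count scenarios PP and mITT agree. This stands, and it is why the point is minor. It does not remove the conflict, because the protocol itself already fixes the PP definition.

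A reader might infer three stronger things.

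- **A second exclusion route through prohibited therapy.** Treatment during the admission could be called a major deviation under Section 8.10.2. No section classes it so; categories are set before lock and unblinding; and these patients are already outside PP. It matters only once the definition is amended, when the wording should close it.
- **An error in handling other missing Day 12 outcomes.** No rule is given for visits missed for other reasons, or for whether a diary entry may be used. Section 12 leaves the full methodology to a SAP finalised before lock and unblinding, and no separate SAP is in the supplied text. This is detail still to be written. The apparently blank Day 12 cell for respiration rate in Table 1 may be an extraction fault, and Sections 9.4.1 and 10.6.4 both record it at that visit.
- **A biased primary result.** The PP definition does not touch the mITT analysis.

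**Conclusion.** The conflict is real and follows directly from the two definitions: patients with a known outcome of failure are removed from the supportive analysis because of that outcome. Severity is minor. With 1 to 6 patients removed per arm, the PP difference lies between 12.2 and 17.5 points against 14.4 in mITT, and within 2.4 points of zero under no effect, with significance unchanged throughout. These sizes rest on assumed removal counts and on the recovery rates in Section 12.6. The direction cannot be known in advance. The reading of the definitions is firm; the size is illustrative.

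**What to change.** Before unblinding, amend the PP definition in Section 12.2 and the Synopsis to: *mITT patients who either completed the Day 12 clinic visit or were classified as treatment failures under the COVID-19 hospitalisation rule, and who had no other major protocol deviation*. Add that treatment given during that admission does not by itself exclude a patient from this analysis set. This concerns analysis membership only, not clinical care.

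The cost is a sentence or two and a small programming change. No new data are needed, and Section 12 lets such changes be documented in the SAP without a protocol amendment. The downside is that PP will contain a few patients with no Day 12 clinic assessment.

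Reminder, not an error: the SAP should say how Day 12 outcomes missing for other reasons are handled, including whether an eDiary entry within one day of Day 12 may be used. If diary data are used, the last diary day needs one statement. The Synopsis lists signs and symptoms "including fever, shortness of breath, cough, and respiratory rate daily from Day 1 to Day 28"; Section 6.1 has patients "be required to complete the eDiary entries from Day 1 through Day 12" and then continues the diary to Day 28; Section 6.1.1 has "daily recording and remote collection of signs and symptoms from Day 1 through Day 11".

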12.3.2 Other Efficacy Analyses

Dichotomous secondary endpoints will be analyzed in the same manner as the primary endpoint. The number of medical follow-up visits tabulated to determine if the endpoint can be considered continuous or ordinal. If the data are continuous the treatment groups will be compared by t-test. If the frequency distribution indicates few numbers of visits (eg 0, 1, 2, and 3 visits) then the analysis will use a chi-squared test to compare treatment groups. The methods for the conduct of the exploratory efficacy analyses will be provided in the SAP. Other *ad hoc* analyses not specified in the SAP may also be performed to further explore the data to aid in the design of future studies.

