	
Primary Efficacy Endpoint:
 
The proportion of patients with clinical recovery at Day 12 will be analyzed using two methods: a 2x2 contingency table and logistic regression. The contingency table will provide unadjusted estimates of the proportions of patients with clinical recovery at Day 12. Copper-Pearson exact 95% confidence intervals around the recovery proportion within each treatment group will be provided. In a logistic regression treatment group will be the primary independent factor, additional covariates will be included in the model if there are sufficient events. Patients who do not have a Day 12 visit due to hospitalization for COVID-19 symptoms will be considered treatment failures
 
Other Efficacy Endpoints:
 
Dichotomous secondary endpoints will be analyzed in the same manner as the primary endpoint. The number of medical follow-up visits tabulated to determine if the endpoint can be considered continuous or ordinal. If the data are continuous the treatment groups will be compared by t-test. If the frequency distribution indicates few numbers of visits (e.g., 0, 1, 2, and 3 visits) then the analysis will use a chi-squared test to compare treatment groups.
 
Safety Endpoints:
 
AEs will be coded using the most recent version of the Medical Dictionary of Regulatory Activities (MedDRA) preferred terms and will be grouped by system, organ, and class (SOC) designation. The incidence of new COVID-19 symptoms not present at screening will be reported separately from other AEs including the maximum severity and time of maximum severity relative to the start of investigational product. The severity, frequency, and relationship of AEs to investigational product will be presented by preferred term by SOC grouping. Listings of each individual AE including start date, stop date, severity, relationship, outcome, and duration will be provided. Each AE (based on preferred terminology) will be counted once only for a given patient. If the same AE occurred on multiple occasions, the highest severity and relationship to investigational product will be assumed. Thus, study participants are not counted multiple times in a given numerator in the calculation of frequencies for a specific AE. Laboratory data and vital signs will be reported as summary statistics and change from baseline by treatment group for the safety population.
 
Justification of Sample Size:
 
Assuming an 85% clinical recovery rate in the TQ group and a 70% clinical recovery rate in the placebo group, sample sizes of 125 per treatment group will achieve 80% power with a two-sided alpha of 0.05 by logistic regression analysis.

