4.2 Secondary

Secondary objectives include determining if TQ:

- Increases the proportion of patients with absence of detectable SARS-CoV-2 virus by RT-PCR at Day 12
- Increases the proportion of patients with absence of clinical symptoms by individual symptom at Day 12
- Decreases the hospitalization rate due to COVID-19 disease by Day 12
- Decreases the number of medical follow-up visits by Day 12

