5.1.2 Secondary

- Proportion of patients with negative SARS-CoV-2 RT-PCR on Day 12
- Hospitalization rates due to COVID-19 symptoms (excluding admittance only for administrative or observations purposes)
- Number of COVID-19-related medical follow up visits (Doctor's office or ER visit)
- Proportion of patients with COVID-19 symptoms at Day 12 by individual symptom

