6.1.3 Randomization

Eligible patients will be randomized at 1:1 ratio to receive TQ or placebo and stratified by site. Randomization will be performed through a centralized, web-based, validated system that automates the assignment of patients to treatment assignment. The randomization scheme will be reviewed and approved by the sponsor or designee. For study medication dispensation, the Investigator or designee will access the randomization system to determine which blinded study medication bottle the patients will be assigned.

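### If visits are few, the follow-up visit count goes to an unordered chi-squared test, which does not target a decrease in visits. Under assumed visit rates it loses about 1 to 17 power points to a mean-score test with sparse categories merged, and 9 to 24 unmerged

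*Combined protocol and SAP*

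**What the plan says.** Section 4.2 states the objective with a direction and a window: "Decreases the number of medical follow-up visits by Day 12". Section 5.1.2 lists the endpoint as "Number of COVID-19-related medical follow up visits" (doctor's office or emergency room) and gives no window.

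The analysis is in Section 12.3.2 and is repeated in the synopsis. First, "The number of medical follow-up visits tabulated to determine if the endpoint can be considered continuous or ordinal". If continuous, the arms are compared by t-test. The other branch opens, in the synopsis wording, "If the frequency distribution indicates few numbers of visits (e.g., 0, 1, 2, and 3 visits"), and "then the analysis will use a chi-squared test to compare treatment groups". No trend, score or rank version is named. There are no category scores, no rule for merging sparse categories and no threshold for what counts as few.

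Section 12 describes the analyses in general terms and leaves full detail to a SAP. No separate SAP text is in the documents. Within Section 12.3.2, only the exploratory methods are expressly left to the SAP; the test for the visit count is stated outright.

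**The concern.** The plan recognises that the count may be ordinal and then names a test that, in its usual form, discards the order. Pearson's chi-squared asks whether the two distributions differ in any way. The objective asks whether visits go down. Two things follow:

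- The test spreads its power over up to three degrees of freedom, so a true reduction is more likely to be missed.
- A significant result does not by itself say that visits fell. No effect estimate is specified that would say so.

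The t-test branch does use the numeric counts, so the two branches answer different questions, and the outcome data decide which one is asked. Few visits per patient is plausible in a non-hospitalised population, so the chi-squared branch may well be the one used.

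**Working it through.** **Inputs from the documents.** Two-sided alpha 0.05 (Section 12.1); 125 per arm (Section 12.6); 1:1 allocation stratified by site (Section 6.1.3); categories 0, 1, 2, 3 (Section 12.3.2). **Assumed:** all visit rates and distributions, because the documents give none.

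**The plan's own figure.** No power is stated for this endpoint. The 80% stated for the primary endpoint reproduces:
- log odds ratio = ln(0.85/0.15) − ln(0.70/0.30) = 0.887
- variance = 1/(125×0.85×0.15) + 1/(125×0.70×0.30) = 0.1008, so SE = 0.318
- 0.887/0.318 − 1.96 = 0.83, which gives 79.8% power.

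**Step 1: order is ignored.** Take an illustrative table of 0/1/2/3 visits: 80/30/10/5 against 95/20/8/2. With equal arms, X² = Σ(a−b)²/(a+b) = 225/175 + 100/50 + 4/18 + 9/7 = 4.794 on 3 df, p = 0.188. Permuting the visit labels leaves this sum unchanged. The mean-score statistic uses the values:
- means 65/125 = 0.52 and 42/125 = 0.336, difference 0.184
- S² = (185 − 250×0.428²)/249 = 0.559
- 0.184²/[0.559×(2/125)] = 3.79 on 1 df, p = 0.052.

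**Step 2: a significant result need not mean fewer visits.** This is a constructed example, not a forecast. The arms have 70/22/6/2% and 77/10/9/4%. Both means are 0.40 (0.22+0.12+0.06 and 0.10+0.18+0.12). Pearson noncentrality = 125×(0.07²/1.47 + 0.12²/0.32 + 0.03²/0.15 + 0.02²/0.06) = 7.6. In simulation Pearson is significant in 64.8% of trials (69.6% with merging), Wilcoxon in 14.4% and the mean-score test in 4.9%.

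**Step 3: benchmark.** If the effect is exactly linear in the scores, 80% power on 1 df needs noncentrality (1.960+0.842)² = 7.849. The same noncentrality gives 70.9% on 2 df and 64.5% on 3 df.

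**Step 4: simulated power.** There were 10,000 trials per scenario, 125 per arm, with 3 or more visits scored 3. Counts were Poisson or negative binomial (NB). Merged means that upper categories are combined until expected counts reach 5. Cells show power (%) as Pearson unmerged / Pearson merged / Wilcoxon / mean-score.

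| Mean visits | Poisson | NB shape 1 | NB shape 0.5 |
|---|---|---|---|
| 0.05 vs 0.15 | 58.7 / 70.3 / 70.7 / 71.7 | 50.1 / 65.3 / 65.9 / 67.4 | 40.6 / 59.3 / 60.3 / 62.8 |
| 0.1 vs 0.25 | 69.3 / 79.2 / 80.5 / 82.3 | 54.3 / 69.2 / 71.4 / 75.6 | 44.8 / 60.4 / 63.0 / 68.6 |
| 0.2 vs 0.4 | 67.1 / 75.8 / 79.8 / 82.7 | 50.7 / 59.2 / 65.7 / 71.6 | 41.4 / 48.5 / 54.3 / 62.0 |
| 0.3 vs 0.5 | 51.2 / 59.5 / 67.2 / 70.8 | 36.6 / 42.3 / 49.1 / 55.7 | 27.9 / 31.0 / 37.3 / 43.2 |
| 0.5 vs 0.8 | 68.1 / 71.7 / 80.1 / 83.5 | 42.6 / 42.8 / 53.4 / 59.5 | 29.5 / 29.5 / 37.8 / 43.8 |
| 0.6 vs 1.0 | 84.9 / 85.6 / 92.7 / 94.3 | 54.1 / 54.1 / 64.6 / 70.6 | 35.9 / 35.9 / 43.9 / 50.9 |

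- Loss against mean-score: 9 to 24 points unmerged, 1 to 17 merged.
- Loss against Wilcoxon: 8 to 20 unmerged, 0 to 11 merged.
- At 0.05 vs 0.15, merging cuts the loss against mean-score from 13.0–22.2 points to 1.4–3.5.
- At 0.3 vs 0.5 the merged loss is still 11 to 13 points.

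A second grid (placebo mean 0.2 to 1.0, rate ratio 0.5 to 0.7, 2,500 trials each, counts capped at 3) gave losses of about 1 to 18 points merged and 1 to 23 unmerged.

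**Step 5: error rates and the proposed test.** Under the null, Pearson rejects in 2.7–5.2% of trials unmerged and 4.5–5.5% merged. A site-stratified mean-score test on actual counts (10 unequal sites assumed, blocks of 4, 4,000 trials per scenario) gains 9 to 23 points over unmerged Pearson and 1 to 22 over merged. Gains near 22 over merged arise at means of 0.5 or more, partly because counts above 3 are not capped. Its type I error is 4.4–5.1%, and the 95% interval for the difference in means covers 93.8–95.6%.

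**The case against.** The strongest reply is that this is under-specification rather than error. The text does not say Pearson, an ordered chi-squared would fit the same words, and one SAP line could settle it. That is true as far as it goes. But the section names a test and no ordered version, and the usual reading of the name is the unordered one.

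Other points that stand, at least in part:

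- Pearson's test does have power against a shift to fewer visits; it simply does not target one. Testing is two-sided, so even a mean-score p-value needs an estimate beside it to show direction.
- The 9-point lower end unmerged is not a floor. At 0.02 vs 0.06 visits, outside the grid above, the unmerged loss is about 4 to 5 points. Part of the unmerged loss also comes from a poor approximation in sparse cells.
- When visits are rarest, merging usually leaves any visit against none. That comparison has a direction and costs little. The loss is zero if every patient has 0 or 1 visits. Merged losses above 10 points mostly need placebo means of about 0.4 or more, which no rate in the documents supports.
- The data were generated as shifts in mean, which suits the mean-score test. Against Wilcoxon the merged loss is smaller.
- No inflated error rate was shown for choosing the branch after tabulation. The objection to that choice is that it leaves the question undefined in advance.

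None of this supplies a reason to prefer the unordered test.

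**Conclusion.** The concern holds. In the few-visits case the named test, read in the ordinary way, ignores order and does not target the stated objective. Under the 18 assumed scenarios the cost against a mean-score test is about 1 to 17 power points if sparse categories are merged and 9 to 24 if they are not; the plan does not say which applies. These sizes rest wholly on assumed Poisson or negative binomial visit rates with 125 per arm. That Pearson's test is blind to order does not depend on those rates. Type I error is not inflated, only one secondary endpoint is affected, and the primary analysis stands. The change should be made before unblinding, but it is not critical to the trial.

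**What to change.** In Section 12.3.2 and the synopsis, delete the chi-squared branch and the choice of test from the tabulated data. Pre-specify one test whatever the distribution: a mean-score (Cochran-Mantel-Haenszel row-mean) test on the visit count, stratified by site to match Section 6.1.3 ("Eligible patients will be randomized at 1:1 ratio to receive TQ or placebo and stratified by site"). Report it with the difference in mean visits per patient and its 95% confidence interval.

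As clarifications only:
- carry the Day 12 window from Section 4.2 into the visit and hospitalisation endpoints in Section 5.1.2, which state none;
- use the same visit scope in both places, since Section 4.2 counts medical follow-up visits and Section 5.1.2 counts only COVID-19-related ones.

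The cost is wording. Section 12 lets changes of method made before database lock and unblinding be documented in the SAP without a protocol amendment. No patients, visits or diary items are added. The drawback is that mean scores count each extra visit equally, so a few patients with many visits weigh more. Wilcoxon limits that weight but had 1 to 8 points less power in these scenarios. Site stratification changed mean-score power by only −1 to +3 points (10 or 25 sites assumed).
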